### 1.2 CURRENT THERAPY

Recombinant hGH (r-hGH) replacement therapy has been used for over 30 years in tens of thousands of patients (primarily children) and has proved to be safe and effective (Ho 2007; Cohen, Rogol et al. 2008). The main therapeutic goal of GH treatment in children with GHD is to enable short children to achieve normal Ht, with early improvement of the psychosocial problems related to short stature. Treatment is by daily SC injection of r-hGH. The Growth Hormone Research Society (GRS) consensus guideline recommends a dose range of 0.025-0.05 mg/kg/day, although in Europe generally a dose of 0.025-0.035 mg/kg/day or 0.7-1.0 mg/m^2 body surface area/day is recommended (according to the Summary of Product Characteristics (SmPC) of Somatropin products). Treatment response is assessed by measurement of Ht and growth velocity and is usually continued until final Ht, epiphyseal closure, or both have been recorded.

The majority of currently available hGH products require daily or every other day SC or intramuscular (IM) injections to maintain hGH blood levels within the effective therapeutic window. The burden of daily administration and its concomitant side effects (e.g., injection site discomfort, transient edema and arthralgia) cause a reduction in compliance (Rosenfeld and Bakker 2008) and can limit the therapeutic utility of existing formulations.

Developments in drug delivery technology have allowed the use of slow-release preparations of GH in humans (Cook, Biller et al. 2002; Kemp, Fielder et al. 2004; Bidlingmaier, Kim et al. 2006). The most successful technology so far has been the encapsulation of GH molecules in poly (D,L-lactic-co-glycolic acid) biodegradable microspheres (Makadia and Siegel 2011). A more recent formulation of GH called LB03002 is an injectable, sustained-release GH suspension of microparticles, consisting of GH incorporated into sodium hyaluronate, which are dispersed in an oil base of medium-chain triglycerides before injection. Hyaluronate is a natural biomaterial found in connective tissues including skin and cartilage and is naturally degraded by hyaluronidase as part of the physiological turnover process. This formulation has been demonstrated to have long acting properties with suitable pharmacokinetic (PK) and pharmacodynamic (PD) profiles (Bidlingmaier, Kim et al. 2006) and efficacy indistinguishable from daily GH treatment in childhood GHD when administered weekly (Peter, Bidlingmaier et al. 2012).

### 1.3 INVESTIGATIONAL THERAPY

MOD-4023 is a long-acting r-hGH for SC administration. It consists of hGH fused to three copies of the CTP of the beta chain of human chorionic gonadotropin (hCG); one copy at the N-terminus and two copies (in tandem) at the C-terminus.

The CTP provides hCG with the required longevity to maintain pregnancy (initial half-life ( $t_{1/2}$ ) ~ 10 hours, terminal  $t_{1/2}$  ~ 37 hours). The beta chain of luteinizing hormone (LH), a gonadotropin that triggers ovulation, is almost identical to hCG, but does not include the CTP. As a result, LH has a significantly shorter half-life in blood (initial  $t_{1/2}$  ~ 1 hour, terminal  $t_{1/2}$  ~ 10 hours). It is, therefore, suggested that the addition of CTP to a protein other than hCG may enable to increase the corresponding protein longevity (Hershkovitz et al. 2015).

Somatrogon is the INN/USAN of MOD-4023 and can be used interchangeably with MOD-4023.

#### 1.3.1 Clinical Studies

MOD-4023 clinical development program includes, apart from the current study, five studies which have been completed. Two (2) Phase 1 studies (CP-4-001, CP-4-007) in healthy adult male volunteers, and Phase 2 studies in GHD adults (CP-4-003) and pre-pubertal GHD children (CP-4-004) were completed. A Phase 3 pivotal study (CP-4-005) in adult patients with GHD is completed and pending final clinical study report. Currently, both CP-4-004 and CP-4-005 are continuing as an OLE until marketing approval.

The Phase 1 study (CP-4-001) was conducted in 24 healthy adult male volunteers CCI

CCI

Another Phase 1 study (CP-4-007) was conducted in healthy male Caucasian and Japanese volunteers. A total of 42 subjects were enrolled and randomized, CCI

The Phase 2, randomized, open-label, multicenter study (CP-4-003) in adults with GHD was designed to assess the safety, tolerability and PK/PD profile of three doses of MOD-4023 administered on a weekly regimen and one exploratory dose on an every other wk regimen. MOD-4023 was administered for a period of four wks in adult GHD patients who were previously on a stable, standard r-hGH treatment for at least six months. Fifty-four (54) patients (48 men and 6 women) were enrolled and completed the study. The clinical adverse effects (such as headache) were consistent with those expected in a GHD population and were mostly of a mild nature.

The completed Phase 2 study (CP-4-004) in a pediatric population was designed to assess the safety, efficacy and tolerability of three MOD-4023 doses as compared to that of a commercially available standard daily r-hGH formulation in up to 56 pre-pubertal children with growth failure due to insufficient secretion of endogenous GH. Fifty-three (53) patients were enrolled and treated with 52 of them finishing the 12-month portion of the study. All three MOD-4023 dose groups demonstrated a growth response comparable to daily r-hGH after 12 months of treatment, as described in detail in the Investigator Brochure (IB), with a safety profile consistent with commercially available r-hGH products.

A Phase 3 pivotal study (CP-4-005) in adult patients with GHD was recently completed. The study is a randomized, parallel-group, multi-center study consisting of a 26-wk double-blind, placebo-controlled (DBPC) period, a 26-wk long-term OLE, in which all patients receive MOD-4023, and a two-wk washout perioda. The starting dose of study drug differed by gender, age and estrogen therapy. Individual dose titration was conducted according to a dose modification plan. The main study, first 12 months, has been completed and is currently being analyzed and reported.

For additional information on clinical studies, please refer to the current version of the IB.

### 1.3.2 Study Rationale

OBL's proprietary CTP technology has enabled the production of a long-acting hGH (MOD-4023), which may obviate the need for the numerous injections currently required in marketed hGH products. As demonstrated in animal models and clinical studies, MOD-4023 may be injected once per wk resulting in similar clinical efficacy as compared to daily injections of r-hGH.

a To obtain blood samples for MOD-4023 Ab assessment and MOD-4023 serum levels.

The purpose of the current Phase 3 study is to demonstrate that weekly MOD-4023 administration in pre-pubertal children with GHD is clinically comparable (non-inferior) to daily Genotropin® administration in terms of safety and efficacy after 12 months treatment duration. The study will be conducted in a randomized, open-label, active-controlled, parallel-group design. After completion of an initial 12 months treatment patients will be eligible to continue treatment with weekly MOD-4023 in a single arm, long term open-label extension (LT-OLE) study for the purpose of collecting additional long term safety and efficacy information.

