## 2. STUDY OBJECTIVES

### Primary Objective:

To demonstrate that weekly MOD-4023 administration is non-inferior to daily Genotropin® administration.

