**Secondary Objective:**

- To evaluate the safety and tolerability of weekly MOD-4023 administration.
- To demonstrate successful operation (single injection) of the MOD-4023 single patient use, multi-dose, disposable pre-filled pen (PEN).
- Evaluation of participant and observer feedback on MOD-4023 device usability.
- To confirm the correct operation of devices returned for evaluation.

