## 8. STATISTICAL ANALYSIS METHOD

### 8.1 SAMPLE SIZE CONSIDERATION

The aim of the main study is to demonstrate that weekly MOD-4023 is not inferior to daily r-hGH administration. Non-inferiority will be claimed if the 2-sided 95% CI for mean treatment difference (MOD-4023 – Genotropin®) in the primary efficacy endpoint will lie entirely above “non-inferiority margin” of -1.8 cm/year.

The following assumptions were made in the sample size calculation:

- 2-sided alpha of 0.05.
- 80 % power.
- Between-patient SD of annual growth rate is 2.5 cm/year in all treatment groups.
- Non-inferiority margin is -1.8 cm/year.
- The true mean treatment difference (MOD-4023 – Genotropin®) is -0.8 cm/year.

With these assumptions, 100 patients per group will provide 80 % power for the non-inferiority test. To allow for an approximate 10 % dropout rate, 110 patients will be randomized to each treatment group (Total N=220 patients).

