### 8.6.6 Safety Analysis

The assessment of safety will be based mainly on the frequency of treatment emergent AEs and on the number of laboratory values that fall outside of pre-determined ranges. Data of all safety endpoints will be listed and tabulated.

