### 8.6.8 Clinical Laboratory Findings

Any CS laboratory data will be reported as an AE. Laboratory data will be reported by analyte for each treatment group. There will not be any hypothesis testing. The laboratory results will be presented at each visit along with the raw change from Baseline for quantitative data. Presence/absence or normal/abnormal results will be summarized as count and percentage. In addition, shift tables summarizing changes from normal to out-of-normal range will be provided.

Descriptive statistics (the number and percentage of patients) of patients with the presence of anti-r-hGH and anti-MOD-4023 Abs will be summarized.

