2. INTRODUCTION

Human growth hormone (hGH) is a 191-amino-acid pituitary protein that stimulates hepatic production and release of insulin-like growth factor-1(IGF-1) into the systemic circulation. IGF-1 is an important mediator in the promotion of linear growth in children and may play a role in the regulation of metabolism and body composition in adults. These factors are regulated through complex feedback mechanisms involving hGH, IGF-1 binding protein-3 (IGFBP-3) and their complexes.

The majority of currently available hGH products require daily or every other day subcutaneous (SC) or intramuscular (IM) injections to maintain hGH blood levels within the effective therapeutic window. The burden of daily administration and its concomitant side effects (e.g., injection site discomfort, transient edema and arthralgia) cause a reduction in compliance (Rosenfeld and Bakker 2008²) and can limit the therapeutic utility of existing formulations.

Somatrogon is a long-acting r-hGH for SC administration. It consists of hGH fused to three copies of the C-terminal peptide (CTP) of the beta chain of human chorionic gonadotropin; one copy at the N-terminus and two copies (in tandem) at the C-terminus. Somatrogon is the International Nonproprietary Name (INN) of somatrogon and can be used interchangeably with MOD-4023.

The purpose of the current Phase 3 study is to demonstrate that weekly somatrogon administration in pre-pubertal children with growth hormone deficiency (GHD) is clinically non-inferior to daily Genotropin® administration in terms of safety and efficacy after 12 months treatment duration. The study will be conducted in a randomized, open-label, active-controlled, parallel-group design. After completion of an initial 12-month treatment, patients will be eligible to continue treatment with weekly somatrogon in a single arm, long-term

open-label extension (LT-OLE) study for the purpose of collecting additional long-term safety and efficacy information.

As the dose selection is driven by evaluating the annual increment in height velocity (HV), the annual HV data obtained for somatropin was compared to Genotropin® results in the Phase 2 study for 52 patients (one patient was mis-diagnosed). Based on 12-month auxology data, it is most likely that a minimum somatropin dose of 0.66 mg/kg/wk will provide an annualized HV comparable to daily hGH at a dose of 34 µg/kg/day.

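### The protocol rationale and SAP introduction announce non-inferiority in safety as well as efficacy, but only 12-month height velocity has a margin and decision rule; safety is described by arm

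*Protocol*

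**What the plan says.** **Purpose.** Protocol 1.3.2 says the trial is meant to demonstrate that MOD-4023 is "clinically comparable (non-inferior) to daily Genotropin ® administration in terms of safety and efficacy after 12 months treatment duration". SAP section 2 states the same purpose without the softer word: "clinically non-inferior to daily Genotropin® administration in terms of safety and efficacy after 12 months treatment duration".

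**Objectives.** The primary objective (protocol synopsis and section 2) is "To demonstrate that weekly MOD-4023 administration is non-inferior to daily Genotropin", with no endpoint named. The safety objective is secondary: "To evaluate the safety and tolerability of weekly MOD-4023 administration".

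**Decision rule.** Protocol 8.1 gives the only margin, "Non-inferiority margin is -1.8 cm/year". The hypotheses and confidence-limit rule in 8.6 and in the synopsis apply it to annual height velocity at 12 months.

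**Safety analysis.** Protocol 8.6.6 says "The assessment of safety will be based mainly on the frequency of treatment emergent AEs", together with counts of out-of-range laboratory values. Section 8.6.7 gives adverse event counts and percentages for each arm. Section 8.6.8 gives laboratory summaries and shift tables, and adds "There will not be any hypothesis testing". Section 8.6.9 tabulates abnormal findings by arm. None of these sections gives a safety margin, a between-arm difference or an interval for one.

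**Which SAP.** Protocol 8.5 promises separate SAPs for the main study and the extension. The SAP reviewed here covers extension data only (its sections 1 and 2) and has no hypothesis testing (its section 5.1).

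**The concern.** Demonstrating non-inferiority requires a stated largest acceptable excess and an interval that rules it out. For height velocity the plan has both. For safety the protocol has neither, yet two background sections put safety under the same verb as efficacy, and the primary objective does not limit the claim to growth. The documents therefore disagree on what the trial may conclude about safety: the rationale promises a demonstration, while the secondary objective and section 8.6 promise a description.

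At stake is how the 12-month safety tables are reported. Under the stated purpose, similar adverse event percentages in the two arms could be presented as demonstrated safety non-inferiority in children, although at this size they would remain compatible with a relevant excess on MOD-4023.

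**Working it through.** **1. The plan's own figure.** Inputs from protocol 8.1: margin -1.8 cm/year, assumed true difference -0.8 cm/year, SD 2.5 cm/year, two-sided alpha 0.05, power 80%.

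- n per arm = 2 x (1.96 + 0.8416)^2 x 2.5^2 / (1.8 - 0.8)^2 = 98.1, rounded up to 99. The plan says 100.
- Power at 100 per arm: the standard error is 2.5 x sqrt(2/100) = 0.354, so power = Phi(1.0/0.354 - 1.96) = 80.7%.

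The stated size reproduces. It was derived for height velocity alone; the protocol states no size or power for safety.

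**2. The two outcomes side by side.**

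| Element | Height velocity | Safety |
|---|---|---|
| Stated purpose (protocol 1.3.2, SAP 2) | demonstrate non-inferiority | demonstrate non-inferiority |
| Formal objective (protocol 2) | primary, endpoint not named | secondary, evaluate |
| Margin | -1.8 cm/year (8.1) | none |
| Hypotheses and decision rule | yes (8.6) | none |
| Between-arm estimate with interval | yes, from ANCOVA (8.6) | none in 8.6.6 to 8.6.9 |

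The rows agree for height velocity once the endpoint is read in from 8.1 and 8.6. For safety, the first row has nothing beneath it to support it.

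**3. What similar percentages would leave open.** The safety set is all dosed patients (8.2.1), and patients who withdraw before the first dose are replaced (4.4), so n is about 110 per arm. The documents give no adverse event rates; those below are assumptions. If both arms are observed at rate p, the simple large-sample 95% interval for the risk difference is zero plus or minus 1.96 x sqrt(2p(1-p)/110):

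- p = 5%: 1.96 x sqrt(0.095/110) = 5.8 points, which includes a doubling (5 points).
- p = 10%: 1.96 x sqrt(0.18/110) = 7.9 points, a near-doubling. A full doubling (10 points) lies just outside.
- p = 20%: 1.96 x sqrt(0.32/110) = 10.6 points, an increase of about half.

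The formula is rough at 5%, where each arm would have only five or six events, but the order of magnitude is clear.

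**The case against.** **The operative text already limits the claim.** Sections 8.1 and 8.6 and the synopsis tie non-inferiority to height velocity and say when it will be concluded. Safety is a secondary objective to be evaluated. The disputed words sit in a rationale and an introduction, and protocol 1.3.2 glosses them as comparable. This stands as far as the primary test goes: nothing in the analysis plan computes or declares safety non-inferiority. It does not remove the contradiction with the stated purpose, nor supply the missing endpoint in the objective itself.

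**The absence is only partly shown.** The main-study SAP was not available and may specify between-arm safety estimates. This stands. A reader might infer that no such estimate is planned anywhere; the documents support that only for the protocol and the extension SAP. A fuller main-study SAP would still not correct the wording in protocol 1.3.2 and SAP section 2.

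**Miss rates overstate the problem.** A reader might infer that the trial will infer safety from a non-significant test and so overlook a doubled event rate more often than not. At 110 per arm, a two-sided 5% Fisher exact test would miss 5% against 10% in 78.6% of trials and 10% against 20% in 52.0%. The documents do not support that reading, because the protocol plans no such test. The figures also depend on the test chosen (an uncorrected chi-square gives 70.2% and 44.1%) and on assumed rates. The by-arm tables would usually show the excess: the chance of seeing no numerical excess on MOD-4023 is about 10% and 2% in the same two cases. The interval widths above are the fairer illustration.

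**Descriptive safety reporting is consistent with an objective to evaluate, and by-arm counts let any reader calculate a difference.** Both are true, and the data safety monitoring board also reviews safety periodically. If the purpose is reworded, the contradiction goes, and the added intervals are then an improvement rather than the repair of an error.

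**Conclusion.** The point holds as an inconsistency between the stated purpose and the plan. Protocol 1.3.2 and SAP section 2 announce a safety conclusion that no objective, margin or analysis in the protocol or the extension SAP can support, and the primary objective leaves the endpoint open. The height velocity comparison, its sample size and its decision rule are not affected.

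The size is illustrative: with about 110 per arm and an assumed 10% event rate seen in both arms, an excess of up to about 8 points remains compatible with the data. This rests on the assumed rate and a large-sample interval; across assumed rates of 5% to 20% the figure runs from 5.8 to 10.6 points. The documents do not show that the sponsor will claim safety non-inferiority, only that the wording would permit it.

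**What to change.** 1. In protocol 1.3.2 and SAP section 2, confine non-inferiority to annual height velocity after 12 months and say that safety and tolerability will be evaluated, as the secondary objective already does. In the synopsis and section 2 of the protocol, name that endpoint in the primary objective.

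2. In protocol 8.6.6 to 8.6.8, or in the main-study SAP if it does not already do so, report the MOD-4023 minus Genotropin difference with a two-sided 95% confidence interval for a short fixed list of outcomes already collected. Examples are any treatment-emergent adverse event, serious adverse events, adverse events leading to discontinuation or dose reduction, injection-site adverse events, and change in HbA1c and fasting glucose. Label this as estimation without testing, and state that the confidence limit on the side of harm, not the absence of a visible difference, describes the excess still compatible with the data.

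The cost is a few sentences and one extra column in the main-study safety tables, with no new data, visits or patients. The downside is a weaker safety statement and intervals that will look wide. If the sponsor does want to claim safety non-inferiority, it would need a named outcome, a justified margin and a sample size to match.

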### 1.3.3 Rationale for Dose Selection

MOD-4023 is a new molecular entity with GH mechanism of action demonstrating reduced receptor affinity, lower specific activity, but with an extended, optimized  $t_{1/2}$ .

The *in vitro* activity and receptor binding affinity of MOD-4023 were established based on comprehensive characterization studies as part of the non-clinical program. MOD-4023, which is comprised of 72.3% net hGH on a molar basis, demonstrated 10 to 20-fold reduction in affinity to GH receptors (GHR) as compared to r-hGH (Biacore analysis). This was further strengthened by two independent cell-based assays analysis indicating that MOD-4023 had a significantly lower biological activity as compared to daily hGH.

Based on the *in vitro* non-clinical pharmacological findings and Phase 2 data it was concluded that any dose comparisons between MOD-4023 and hGH that were initially done on molar basis were not reflective of the biological effect of the molecule. Therefore, the selection of MOD-4023 dose for the Phase 3 studies was determined by safety parameters and in particular by the clinical effect, i.e. HV.

This assumption was confirmed during the Phase 2 pediatric study, when monitoring the IGF-1 response. Two (2) of the doses of MOD-4023 administered in the Phase 2 study, 0.48 and 0.66 mg/kg/wk, resulted in comparable IGF-1 and IGFBP-3 profiles to that of Genotropin® administered daily at a dose of 34 µg/kg/day. These two doses of MOD-4023 were shown to maintain IGF-1 serum levels, with values that were in the middle part of the gender and age-adjusted normal range (~0 SDS). MOD-4023 dose of 0.25 mg/kg/wk failed to maintain normal IGF-1 serum levels mainly during the second part of the wk, indicating that IGF-1 levels will be at the lower part of the normal range or even below it with the use of this dose on weekly basis. These observations were further confirmed by the population-based model. Mean IGF-1 SDS values for Cohort 3 and Cohort 2 (MOD-4023 dose of 0.66 and 0.48 mg/kg/wk, respectively) were around 0 SDS IGF-1, and consistently much lower than 0 for Cohort 1 (0.25 mg/kg/wk). Therefore, it is proposed that MOD-4023 doses of 0.48 and 0.66 mg/kg/wk are more likely to result in IGF-1 and IGFBP-3 levels that are comparable to daily Genotropin® injections within the well-established suitable safety range with no direct correlation to GH molar content.

As the dose selection is driven by evaluating the annual increment in HV, the annual HV data obtained for MOD-4023 was compared to Genotropin® results in the Phase 2 study for 52 patients (one patient was mis-diagnosed). Based on 12-month auxology data, it is most likely that a minimum MOD-4023 dose of 0.66 mg/kg/wk will provide an annualized HV comparable to daily hGH at a dose of 34 µg/kg/day.

## 2. STUDY OBJECTIVES

### Primary Objective:

To demonstrate that weekly MOD-4023 administration is non-inferior to daily Genotropin® administration.

